7.6. Infected Lesions

EBS lesions that become infected (*i.e.*, EBS lesions that require therapy to treat an infection) during the course of the study should be managed following the investigator's routine practice and all concomitant therapies reported in the eCRFs.

No study medication applications should be made to infected lesions. If any EBS lesions are not treated with study medication because they are infected, this situation must be noted as an adverse event. If the subject does not apply the study medication once daily to all EBS lesions for more than seven consecutive days, the subject must be withdrawn from treatment.

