7.7. Subject Discontinuation from the Study

Subjects/caregiver will be informed that the subjects are free to withdraw from the study at any time and for any reason. Subjects also have the option to withdraw from treatment at any time. Subjects that withdraw from treatment will continue to follow their visit schedule but will no longer apply the study medication.

The investigator may remove a subject from the study if, in the investigator's opinion, it is not in the best interest of the subject to continue the study. If the subject does not apply the study medication once daily to all EBS lesions for more than seven consecutive days, the subject must be withdrawn from treatment.

Examples of other reasons subjects may be discontinued from the study are:

- A change in compliance with an inclusion or exclusion criterion
- Occurrence of AEs
- Occurrence of pregnancy
- Use of a prohibited therapy
- Failure to maintain the required application frequency.

In case of premature discontinuation of study participation, efforts will be made to perform all final study day assessments. The date the subject is withdrawn from the study and the reason for discontinuation will be recorded on the subject's eCRFs. All withdrawn subjects with ongoing AEs will be followed as appropriate.

The investigator must immediately (within 24 hours) notify the Castle Creek Pharmaceuticals, LLC assigned study monitor of a subject discontinuation.

The study may be discontinued at the discretion of Castle Creek Pharmaceuticals, LLC. Some examples of reasons for discontinuation are the occurrence of the following:

- Increased frequency, severity or duration of known AEs
- Medical, regulatory or ethical reasons affecting the continued performance of the study
- Difficulties in the recruitment of subjects.

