8.8.8. Dose modification

Subjects/caregivers should not modify the study medication application procedure or frequency without approval from the investigator or designee.

If any significant study medication intolerance or safety issue occurs the investigator or designee may direct the subject/caregiver to reduce the study medication application frequency as determined by the Investigator.

If the subject does not apply the study medication once daily to the assessment area for more than seven consecutive days, the subject must be removed from the study.

Moderate-to-severe diarrhea has been observed in some patients administered oral diacerein for the treatment of osteoarthritis:

- Moderate diarrhea: 5-10 watery stools per day
- Severe diarrhea: >10 watery stools per day.

Study medication applications should be discontinued if the subject experiences moderate or severe diarrhea.

Study medication should also be discontinued if the subject experiences any instance of diarrhea with bleeding and there is no clear medical rationale for the occurrence.

The diarrhea must be reported as an adverse event in the eCRF. These subjects should be withdrawn from the study.

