4. ANALYSIS POPULATIONS

4.1. Intent-to-Treat Population

The Intent-to-Treat (ITT) Population will consist of all randomized subjects who are dispensed study medication. All efficacy analyses will be conducted using the ITT population. Subjects will be included in the treatment group to which they were randomized.

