5.2. Assessment Windows

In the descriptive statistics of safety and efficacy endpoints, only measurements from scheduled visits will be used if values are available. If no values from a scheduled visit are available but values from unscheduled visits are available, the values from the unscheduled visit closest to the target date for that visit will be used for the summary statistics. The date of an unscheduled visit will be used to assign the unscheduled visit to the nearest scheduled visit date.

For analysis purposes, if the event date is on or after the first treatment date, the study day is defined as follows:

$$\text{Study Day} = \text{Event date} - \text{First treatment date} + 1$$

Therefore, the day of the first treatment will be Day 1. If the event date is prior to the first treatment date, the addition of 1 will not be included in the calculation; thus, there will be no Day 0.

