5.5. Non-Date Values

Every effort will be made to obtain required data at each scheduled evaluation from all subjects who have been enrolled.

For the primary analysis of the primary efficacy endpoint (proportion of subjects who achieve $\geq 60\%$ reduction in BSA of EBS lesions with the Assessment Area from Baseline to Visit 6/Week 8), subjects whose status at Week 8 is unknown will be defined to be a non-success/non-responder.

For sensitivity analysis of this endpoint, the following analyses will be performed:

1. Subjects with missing values at Week 8 in the Diacerein treatment group will be imputed as a success, while all subjects in the Placebo treatment group will imputed as a non-success.
2. Subjects with missing values at Week 8 in the Diacerein treatment group will be imputed as a non-success, while all subjects in the Placebo treatment group will imputed as a success.
3. Subjects with missing values at Week 8 will be imputed using multiple imputation (MI) under the assumption of missing at random (MAR). Based on the imputed value at Week 8, the subjects will be assigned accordingly as either a success or non-success.

Missing values for the BSA of EBS lesions within the Assessment Area will be imputed using multiple imputation methodology in two steps. Initially, ten datasets will be generated containing imputed values for non-monotone missing values in the original dataset. The variables used to guide this imputation will include the following: treatment group, age group (<8 and ≥ 8 years old), genotype (KRT5/KRT14 and Other), and BSA

of EBS lesions in the Assessment Area at Baseline, Week 1, Week 4, Week 8, and Week 16. In this step it will be assumed that any intermediate missing data points are MAR. In the second step, the remaining monotone missing values will be imputed. The same variables will be used to guide the imputation as in the first step.

For each imputation dataset, the proportion of subjects who achieve success will be analyzed using the Cochran-Mantel-Haenszel test described in Section 7.1 below. A log transformation will be performed to normalize the relative risk estimates and the standard error of the transformed estimate will be obtained from the log-transformed confidence limits for the relative risk estimate. The results from these ten analyses will be combined and then back-transformed to the original log scale. The corresponding relative risk estimate and confidence interval will be presented.

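### Missing more than seven days of application means withdrawal from treatment with visits continuing in Protocol 7.6 and 7.7, but removal from the study in 8.8.8

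*Protocol*

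**What the plan says.** Three places in the current protocol set a consequence for more than seven consecutive days without once-daily application.

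- Protocol 7.6 (Infected Lesions) and 7.7 (Subject Discontinuation from the Study) carry the same sentence. For failure to apply the medication "once daily to all EBS lesions for more than seven consecutive days, the subject must be withdrawn from treatment".
- Protocol 8.8.8 (Dose modification) has a parallel sentence with a different ending: "once daily to the assessment area for more than seven consecutive days, the subject must be removed from the study".

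Protocol 7.7 also says what withdrawal from treatment entails: "Subjects that withdraw from treatment will continue to follow their visit schedule but will no longer apply the study medication". For a subject who leaves the study early it promises less: "In case of premature discontinuation of study participation, efforts will be made to perform all final study day assessments". Its list of further reasons for which a subject may be discontinued from the study includes "Failure to maintain the required application frequency".

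On the analysis side, SAP 4.1 states: "The Intent-to-Treat (ITT) Population will consist of all randomized subjects who are dispensed study medication". SAP 5.5, 7.1 and 7.2 count a subject whose Week 8 status is unknown as a nonresponder on both the primary endpoint (at least 60% reduction in BSA at Week 8) and the key secondary endpoint (IGA success at Week 8).

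**The concern.** One event has two mandatory outcomes. Under 7.7 the subject stops the ointment but is still seen at Visit 6, so Week 8 BSA and IGA are measured. Under 8.8.8 the subject leaves, and if that happens well before Visit 6 there may be no Week 8 value. The subject remains in the ITT population either way. Which section a site happens to read can therefore decide whether an outcome is observed or set to nonresponse by rule. In a trial of about 80 subjects at about 20 centers, different sites could resolve the conflict differently.

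**Working it through.** No figure in the plan is in dispute, so the check compares the texts and then traces the consequence into the analysis.

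**1. The sentences side by side.**

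| Section | Trigger | Scope | Consequence | Visits afterwards |
|---|---|---|---|---|
| 7.6 | more than 7 consecutive days | all EBS lesions | mandatory withdrawal from treatment | not stated; 7.7 supplies it |
| 7.7 | more than 7 consecutive days | all EBS lesions | mandatory withdrawal from treatment | continue |
| 8.8.8 | more than 7 consecutive days | Assessment Area | mandatory removal from the study | end |

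**2. A test case.** Take a subject with active lesions whose last application is on Day 20 and who applies nothing on Days 21 to 28. That is 8 missed evenings, and 8 > 7. Assessment Area lesions are EBS lesions, so the subject meets all three triggers. The subject cannot both continue visits and be out of the study.

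**3. Is there a tie-breaker?** The 7.7 list item on application frequency is discretionary, so it does not reconcile two mandatory rules. SAP 5.5 says how to treat an unknown Week 8 status, not whether the subject should have left. SAP 12, Table 2, lists the protocol sections affected by the SAP changes; 7.6, 7.7 and 8.8.8 are not among them. Nothing ranks one section over another.

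**4. What happens to Week 8.** The lapse is found at Visit 4 (Day 29). Under 7.7, Visits 5 to 8 still take place and Day 57 is measured. Under 8.8.8 the exit assessment falls on Day 29. For unscheduled visits SAP 5.2 says: "The date of an unscheduled visit will be used to assign the unscheduled visit to the nearest scheduled visit date". The midpoint between Visit 5 and Visit 6 is (43 + 57)/2 = Day 50, so an exit before Day 50 is nearer Visit 5 or an earlier visit and gives no Week 8 value. An exit after Day 50 could be assigned to Week 8. SAP 5.2 is written for descriptive statistics, and applying it to the primary endpoint is an assumption. Hence Week 8 *may* be unknown.

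**5. Size per subject.** 80 subjects randomized 1:1 gives 80/2 = 40 per arm. Let y = 1 if the subject would have been a Week 8 success and y = 0 if not. Counting the subject as a nonresponder changes the arm's success proportion by (0 − y)/40:

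- y = 1: −1/40 = −2.5 percentage points
- y = 0: no change

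If the sample size were raised to the maximum of 200 in SAP 10 (100 per arm), the first figure would be 1/100 = 1.0 point.

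**6. Sensitivity analyses (SAP 5.5).** In analysis 2, "Subjects with missing values at Week 8 in the Diacerein treatment group will be imputed as a non-success"; analysis 1 does the opposite. Reading the placebo wording in both as applying to missing values only, each lost Week 8 value widens the spread between the two analyses by 1/40 = 2.5 points of treatment difference. That is the distance between two extremes, not a shift in the primary result. Analysis 3 (multiple imputation under missing at random) uses BSA from other visits and so recovers part of the information. It replaces a measurement with a prediction, and it does not alter the primary analysis.

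**7. What else is lost.** Removal also ends the later visits. These include Week 16 BSA and IGA, which are other secondary endpoints with no imputation under SAP 5.5, and the follow-up laboratory tests and ECG at Visit 8.

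**The case against.** Four points can be made for leaving the text alone.

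*The two orders are compatible, since leaving the study also ends treatment.* Taken alone, the seven-day sentences can both be obeyed. The clash comes through the 7.7 sentence on continued visits, which directly follows a sentence on the subject's option to stop treatment. Applying it to a mandatory withdrawal is an inference. It is the natural one: the sentence is not limited to voluntary cases, and the same section orders withdrawal from treatment in the next paragraph.

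*Section 7.7 may itself intend study exit.* It is headed as discontinuation from the study, and the list after the seven-day rule is introduced as giving *other* reasons. That suggests the seven-day rule may have been thought of as a ground for leaving. This stands, and it leaves the sponsor's intent open.

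*The triggers differ.* A subject who neglects only new lesions outside the Assessment Area meets 7.6 and 7.7 but not 8.8.8. That narrows the set of affected subjects but does not help the subject with active lesions who applies nothing.

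*Removal in 8.8.8 may be loose wording for stopping treatment.* Possibly. However, in its paragraphs on diarrhea 8.8.8 itself treats stopping applications and leaving the study as separate steps, so a site that takes it literally is not misreading it.

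**Conclusion.** The inconsistency is real and minor. For a subject who applies no study medication for more than seven consecutive days, the protocol orders withdrawal from treatment in two sections, with continued visits in 7.7, and removal from the study in a third. It does not say which governs. Following 8.8.8 before Visit 6 can turn a measurable Week 8 BSA and IGA into a nonresponse by rule. Per subject this costs the arm 2.5 percentage points or nothing, assuming 40 per arm. No expected effect on the result is given, because the documents state no rate of missed applications.

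Three stronger readings are tempting and are not supported:

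- *The arm with more removals always has its success rate lowered.* It is lowered or unchanged: a removed subject who would have failed at Week 8 changes nothing. The documents also do not show which arm would have more removals.
- *Most lapses would cost the Week 8 value, because most of the treatment period lies before Visit 6.* A share of calendar days on which a lapse could begin is not a share of subjects.
- *Section 8.8.8 is plainly the mistaken one.* The lead-in to the 7.7 list leaves that open. The preference for 7.7 rests on keeping measured outcomes for the ITT population, not on proof of intent.

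Whether infection pauses or investigator-directed frequency reductions count toward the seven days is a question for the sponsor and is not part of this point.

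**What to change.** In Protocol 8.8.8, replace the removal clause of the seven-day sentence with: *must be withdrawn from treatment and continue the visit schedule (Section 7.7)*. Leave the scope of each trigger as it is. Harmonizing scope is not needed to remove the contradiction, and extending 8.8.8 to all treated lesions could let one infected lesion outside the Assessment Area trigger it.

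If the sponsor does intend removal from the study, 7.6 and 7.7 need correcting instead, with the loss of Week 8 and Week 16 data accepted knowingly.

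The cost is one clause. It can go into the protocol amendment that SAP 12 already plans, but it must be added explicitly because Table 2 does not list these sections. A short memo to sites would cover the interval. No new visit or form is needed. The small downside is holding the remaining scheduled visits for subjects whom a site would otherwise have removed.

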7.9. Replacement Subjects

Subject enrollment will continue until approximately 80 subjects have been randomized. Subjects who are randomized and do not complete the study will not be replaced.

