8.2.6. Visit 6 (Week 8/Day 57); end of the treatment period

This visit must occur 8 weeks/56 days (± 4 days) after Visit 2.

At this visit, the investigator or designee will perform the following procedures:

1. Query the subject/caregiver in a non-directive manner about any changes in the subject's health since the previous visit and report all AEs on the appropriate form
2. Query the subject/caregiver about any changes in the subject's concomitant therapies since the previous visit and report changes on the appropriate form
3. Confirm the subject continues to comply with all study restrictions, is eligible to continue in the study and has followed all study instructions
4. Conduct a physical examination
5. Measure vital signs
6. Perform a urine pregnancy test for WOCBP
7. Identify any new lesions that appeared since the last visit
8. Determine BSA of EBS lesions in the Assessment Area and new lesions (if new lesions exist), as well as EBS lesions that are not being treated (e.g. $>30\%$ BSA or lesions that are occluded) using the palmar method
9. Measure the LSA of the Reference Lesion
10. Perform the IGA evaluation on the Assessment Area
11. Collect blood & urine samples for clinical laboratory tests
12. Take standardized color photographs
13. Collect and weigh all study medication as appropriate
14. Dispense a blister lancing kit and instructions to the subject/caregiver if needed
15. Review the study instructions, including eDiary, use of body charts and approved bland, non-medicated, emollient/moisturizer use, with the subject/caregiver
16. Perform ECG
17. Schedule Visit 7 for Week 12/Day 84.

The investigator will mark the general location of all the EBS lesions on the appropriate body chart(s) at each study visit.

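### Protocol 8.8.8 takes a subject off study for a lapse of more than seven days on the Assessment Area, while 7.7 keeps such a subject on the visit schedule, so an obtainable Week 8 outcome can become an imputed failure

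*Protocol*

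**What the plan says.** Protocol 8.8.8 (Dose modification) addresses a subject who "does not apply the study medication once daily to the assessment area". If this lasts "for more than seven consecutive days, the subject must be removed from the study".

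Protocol 7.6 (Infected Lesions) addresses a lapse of the same length in once-daily application to all EBS lesions: "for more than seven consecutive days, the subject must be withdrawn from treatment". Protocol 7.7 (Subject Discontinuation from the Study) repeats that rule: "once daily to all EBS lesions for more than seven consecutive days, the subject must be withdrawn from treatment". Section 7.7, but not 7.6, also states what treatment withdrawal means for follow-up: "Subjects that withdraw from treatment will continue to follow their visit schedule but will no longer apply the study medication". The same section lists failure to keep up the application frequency among reasons for which a subject may be discontinued from the study. For early study exit it says "efforts will be made to perform all final study day assessments". Protocol 7.9 adds: "Subjects who are randomized and do not complete the study will not be replaced".

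The SAP defines ITT as all randomized subjects who were dispensed medication (4.1). Unknown Week 8 status is a non-response for the primary BSA endpoint (5.5, 7.1) and for the key secondary IGA endpoint (7.2). The Visit 8 BSA and IGA responses are other secondary endpoints with no imputation (3.1.3, 5.5). The Per Protocol set requires BSA and IGA at Week 8 (4.3). The table of changes from the protocol in SAP 12 does not mention the lapse rule.

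**The concern.** The Assessment Area is made up of EBS lesions to be treated (protocol 9.1.2), so a lapse there satisfies both triggers. A site that follows 8.8.8 ends the subject's participation. A site that follows 7.7 stops the ointment and keeps the visits. Neither document says which section prevails.

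The choice reaches the confirmatory analysis. A subject removed before Week 8 stays in the denominator, is not replaced, and counts as a failure on both confirmatory endpoints if no Week 8 assessment is made. The same subject handled under 7.7 would be on schedule for an observed BSA and IGA. Visit 8 outcomes can be lost in the same way, and without Week 8 values the subject also leaves the Per Protocol set.

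The trigger is not confined to careless subjects. Infected lesions must not be treated (7.6), and 8.8.8 lets the investigator cut the application frequency for intolerance or a safety issue. Read literally, either can produce more than seven days without once-daily application in a subject who is following instructions. Removal could therefore be related to disease course or treatment and need not be balanced between arms.

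**Working it through.** **Step 1: the rules side by side**

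| Section | Trigger (more than seven consecutive days) | Consequence | Visits |
|---|---|---|---|
| 7.6 | not once daily to all EBS lesions | off treatment (mandatory) | not stated |
| 7.7 | not once daily to all EBS lesions | off treatment (mandatory) | continue, without medication |
| 7.7, list of examples | application frequency not maintained | off study (permitted) | final-day assessments attempted |
| 8.8.8 | not once daily to the Assessment Area | off study (mandatory) | end |

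Leaving the study also ends treatment, so the two mandatory clauses taken alone could both be obeyed. What cannot be obeyed together is 8.8.8 and the continued-visits sentence in 7.7.

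**Step 2: the plan's own power figure**

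Inputs from SAP 11: 80 subjects, response 60% versus 30%, two-sided alpha 0.049. With 1:1 allocation (SAP 2.2), n = 40 per arm. Pooled-variance formula, with z = 1.969 and p̄ the mean of the two rates:

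power = Φ{ [(p1 − p2) − z√(2p̄(1 − p̄)/n)] / √([p1(1 − p1) + p2(1 − p2)]/n) }

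= Φ[(0.300 − 0.219)/0.1061] = Φ(0.764) = 77.7%. SAP 11 states 77%, so the figure reproduces.

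**Step 3: illustrative effect of imputed failures**

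The documents give no lapse rate. Assume a fraction d = 5%, 10% or 15% of each arm lapses (2, 4 or 6 of 40).

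- A. All lapsers are imputed as failures but would have responded at 60%/30%. The rates become 0.6(1 − d) and 0.3(1 − d).
- B. As A, but only half of the lapsers are removed. The rates become 0.6(1 − d/2) and 0.3(1 − d/2).
- C. All lapsers are observed, and active lapsers respond at the control rate. The rates become 0.6(1 − d) + 0.3d and 0.3.

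| d | A: power | B: power | C: power | C − A (points) |
|---|---|---|---|---|
| 5% | 73.7% | 75.8% | 73.4% | −0.4 |
| 10% | 69.5% | 73.7% | 68.6% | −0.9 |
| 15% | 65.2% | 71.6% | 63.6% | −1.6 |

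Example for A at d = 10%: 0.54 versus 0.27 gives Φ[(0.270 − 0.216)/0.1055] = Φ(0.511) = 69.5%.

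The treatment difference is 0.3(1 − d) in both A and C, that is 28.5, 27.0 and 25.5 points. If active lapsers respond at the control rate, imputing all lapsers as failures gives the rates in A and observing them gives those in C. Observing them then changes neither the difference nor, to any useful extent, the power.

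**Step 4: is A a worst case?**

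No. Hold the overall rates at 60%/30% and let lapsers respond at 80% (active) and 30% (control), for example because subjects stop once lesions have healed. This is an assumption, not a finding. With 10% lapsing and all imputed as failures, the rates are 0.60 − 0.10 × 0.80 = 0.52 and 0.30 − 0.10 × 0.30 = 0.27, and power is 62.9%, below the 69.5% in A. At 15% the rates are 0.48 and 0.255, and power is about 55%, against 65.2%.

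**Step 5: unequal removal**

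With lapsers otherwise responding at 60%/30%, removing 10% of active and 5% of control subjects gives 0.54 versus 0.285 and 64.1% power. Removing 5% and 10% gives 0.57 versus 0.27 and 78.4%. The effect can go either way.

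**The case against.** The strongest objection is that the practical effect is unproven. There is no lapse rate in the documents. The 60%/30% rates were set for the Week 16, 40%-reduction endpoint, and SAP 11 says no data exist for the current one. Step 3 shows that even the sign of the power effect depends on how lapsers respond. This stands. The textual conflict is certain, but its size is not.

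A reader might infer that every removal under 8.8.8 loses the Week 8 outcome. The documents do not support that. Section 7.7 asks for exit assessments, and at Visit 6 staff are told to "Confirm the subject continues to comply with all study restrictions, is eligible to continue in the study and has followed all study instructions" at the same visit where BSA and IGA are measured, so a lapse first found there need not cost the data. The safeguard is partial, however. Adherence is also reviewed at the earlier treatment visits, an exit visit before Week 8 is not clearly a Week 8 status, and SAP 5.2 assigns unscheduled values to visits only for descriptive statistics. The sensitivity analyses in SAP 5.5 show how much missing values could matter but do not recover them.

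A reader might also infer that 7.6 promises continued visits. It does not; only 7.7 does. There the sentence directly follows the option of voluntary withdrawal, so applying it to mandatory withdrawal is a reasonable reading rather than an explicit rule.

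Finally, changing 8.8.8 alone would leave the permissive example in 7.7, under which a site could still take the same subject off study. That is correct, and the remedy has to cover it.

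**Conclusion.** The inconsistency is real and should be corrected. For a lapse of more than seven days on the Assessment Area, 8.8.8 requires study exit, while 7.7 most naturally keeps the subject on the visit schedule. Following 8.8.8 can convert an observable Week 8 BSA and IGA into imputed failures, and can lose the Visit 8 outcomes.

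On the planning rates, with equal lapse in both arms and every lapser's outcome lost, power would be 73.7%, 69.5% or 65.2% at 5%, 10% or 15% lapse, against 77.7% with none. These figures are neither a forecast nor an upper bound on the loss: it is larger if lapsers are more often responders, and the fix gains no power if active lapsers respond at the control rate. A claim that the trial is underpowered or biased in a known direction because of 8.8.8 would go beyond the documents. What the correction secures is less avoidable missing data, and an outcome status that does not depend on which section a site happened to follow.

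**What to change.** Four linked wording changes in the protocol:

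1. In 8.8.8, change the consequence of the seven-day lapse from study exit to withdrawal from treatment. Refer to 7.7 for continued visits, naming the Visit 6 and Visit 8 BSA and IGA.
2. In 7.7, delete failure to maintain application frequency from the reasons for study discontinuation, or move it to treatment withdrawal.
3. In 7.7, state that continued visits apply to mandatory as well as voluntary treatment withdrawal.
4. Use the Assessment Area as the single seven-day trigger in 7.6, 7.7 and 8.8.8, so that one infected lesion elsewhere does not force a subject off treatment.

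Leave the study exits for diarrhea (8.8.8), pregnancy (9.2.7, 10.6) and unblinding (8.11.2) as they are.

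No visit or assessment is added. The cost is a small amendment needing ethics approval at about 20 international centers. SAP 12 already foresees a protocol amendment that can carry it.

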7.1. Primary Efficacy Analysis

Descriptive summaries of the proportion of subjects who achieve $\geq 60\%$ reduction in BSA of EBS lesions will be presented by treatment group at each visit.

The primary endpoint is the proportion of subjects who achieve $\geq 60\%$ reduction in BSA of EBS lesions from Baseline to Visit 6 (Week 8). Subjects whose status at Visit 6 is unknown will be defined to be nonresponders. The primary analysis will be conducted using the Cochran-Mantel-Haenszel (CMH) test, stratified by genotype (KRT5/KRT15 and Other) and age group (<8 and ≥ 8 years old). Estimated relative risk, associated 95% confidence interval (CI), and p-values will be provided.

At the final analysis, the treatment groups will be compared using a two-sided test at the $\alpha=0.049$ level of significance in order to account for the alpha spent in the Interim Analysis as described in Section 10 below.

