7.2. Key Secondary Efficacy Analysis

The key secondary endpoint is the proportion of subjects achieving success on the IGA of the Assessment Area, where success on the IGA is defined as at least a 2-point reduction from Baseline to Visit 6 (Week 8). Subjects whose status at Visit 6 is unknown will be defined as non-responders. The key secondary endpoint will be analyzed using the CMH test, as described for the primary analysis. However, if the primary analysis is not statistically significant, then the results for the key secondary endpoint will be exploratory rather than confirmatory. This fixed sequence testing procedure maintains the overall level of significance for the primary and key secondary endpoints.

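### Protocol 8.8.8 removes a subject from the study after more than seven days without study medication, while 7.6 and 7.7 only withdraw that subject from treatment, so collection of the Week 8 outcome depends on which section a site follows

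*Protocol*

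**What the plan says.** **Seven-day rule.** Protocol 8.8.8 concerns once-daily application to the assessment area. A subject who misses it "for more than seven consecutive days, the subject must be removed from the study". Section 7.6, on infected lesions, concerns application to all EBS lesions: a subject who misses it "for more than seven consecutive days, the subject must be withdrawn from treatment". Section 7.7 repeats the 7.6 rule and adds: "Subjects that withdraw from treatment will continue to follow their visit schedule but will no longer apply the study medication".

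**Diarrhea rule.** 8.8.8 stops study medication for moderate or severe diarrhea, and for bloody diarrhea without a clear medical explanation. It then continues: "The diarrhea must be reported as an adverse event in the eCRF. These subjects should be withdrawn from the study".

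**Leaving the study.** 7.7 lists reasons for which a subject may be discontinued from the study. They include adverse events and failure to keep up the application frequency. On premature exit, "efforts will be made to perform all final study day assessments".

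**Scoring.** The SAP's primary endpoint is at Visit 6 (Week 8). SAP 5.5 states that "subjects whose status at Week 8 is unknown will be defined to be a non-success/non-responder". SAP 7.1 repeats this for the primary analysis, and SAP 7.2 applies it to the key secondary endpoint: "Subjects whose status at Visit 6 is unknown will be defined as non-responders". The ITT population (SAP 4.1) keeps every randomized subject who was dispensed medication. Other secondary endpoints, including Week 16 BSA and IGA success, receive no imputation (SAP 5.5).

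**The concern.** For the same event, one section ends participation and two sections end only treatment. Sites will differ in what they do, and the choice decides whether the Week 8 and Week 16 outcomes are observed.

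The trigger needs neither diarrhea nor poor compliance. Section 7.6 forbids application to infected lesions, so an infection of the assessment area lasting more than a week can set it off. Section 8.8.8 also allows the investigator to reduce application frequency for intolerance. Read literally, its next sentence removes a subject whose approved reduction lasts eight days.

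At stake are observed outcomes being replaced by assigned failures on both confirmatory endpoints, Week 16 data going missing, and scheduled laboratory tests and ECGs stopping. With about 40 subjects per arm and no replacement of non-completers (Protocol 7.9), each subject is 2.5% of an arm.

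**Working it through.** **1. Do the two seven-day rules reach the same subject?**

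| | 8.8.8 | 7.6 and 7.7 |
|---|---|---|
| Area | assessment area | all EBS lesions |
| Duration | more than 7 consecutive days | more than 7 consecutive days |
| Force | must | must |
| Result | leaves the study | leaves treatment, visits continue |

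Assessment-area lesions are among all EBS lesions, so a subject who meets the 8.8.8 trigger also meets the other one. The two results cannot both be carried out.

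**2. Is the Week 8 outcome lost?** An exit assessment is attempted at the time of leaving. SAP 5.2 assigns an unscheduled visit to the nearest scheduled visit. Visit 6 is Day 57 and its neighbours are Days 43 and 85, so the midpoints are (43 + 57)/2 = Day 50 and (57 + 85)/2 = Day 71. An exit assessment between about Day 51 and Day 70 might therefore count as Visit 6, although that rule is worded for descriptive statistics. Earlier exits have no Week 8 status and are scored as failures.

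**3. What else is lost?** For an exit at Week 2, the visit descriptions in Protocol 8.2 give five remaining BSA and IGA ratings (Visits 4 to 8), three laboratory draws (Visits 4, 6, 8) and two ECGs (Visits 6, 8). Each becomes at most one.

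**4. Illustrative power.** Inputs from SAP 11: 60% vs 30%, 80 subjects (40 per arm), two-sided alpha 0.049, stated power 77%. The critical value is z = 1.9686. With pooled variance under the null,

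power = Φ{[(p1 − p2)√n − z√(2p̄(1 − p̄))] / √(p1(1 − p1) + p2(1 − p2))}, where p̄ = (p1 + p2)/2.

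No loss: p̄ = 0.45, so [0.3 × 6.3246 − 1.9686 × 0.7036]/0.6708 = 0.764 and power is 77.7%. This reproduces the SAP's 77%.

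The loss rates below are assumptions, because the documents give none. Lost subjects are scored as failures. Kept subjects are assumed to respond at the 30% control rate.

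| Loss before Visit 6 | Rates if lost | Power if lost | Rates if kept | Power if kept |
|---|---|---|---|---|
| 2.5% active only (1 of 40) | 0.6 × 0.975 = 0.585 vs 0.300 | 73.4% | 0.585 + 0.025 × 0.3 = 0.5925 vs 0.300 | 75.6% |
| 5% active only (2 of 40) | 0.6 × 0.95 = 0.570 vs 0.300 | 68.6% | 0.570 + 0.05 × 0.3 = 0.585 vs 0.300 | 73.4% |
| 5% in both arms | 0.570 vs 0.3 × 0.95 = 0.285 | 73.7% | 0.585 vs 0.300 | 73.4% |

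If kept subjects responded at their own arm's full rate, power would return to 77.7%, which is a ceiling. In the last row, keeping subjects who respond at the control rate lowers power by 0.4 points before rounding (0.7372 to 0.7336).

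**The case against.** **The diarrhea rule.** A reader might infer that the diarrhea sentence also contradicts 7.7. It does not. 7.7 allows discontinuation from the study for adverse events, and 8.8.8 says should rather than must. It is a cautious safety choice in a trial that enrolls from age 4. What can be said is narrower: stopping the ointment already ends exposure, so leaving the study mainly ends data collection.

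**7.7's own list.** 7.7 names failure to maintain application frequency as a possible reason to leave the study. This softens the conflict, but a permission does not reconcile two mandatory instructions. It does mean that editing 8.8.8 alone would be incomplete.

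**Safety follow-up.** A reader might infer that affected subjects are lost to safety follow-up. The protocol does not support that. Moderate to severe diarrhea is an event of special interest and is followed until it subsides, stabilizes or becomes chronic (10.4.3, 10.5.1.2). Adverse events are collected for at least 30 days after the last application, and clinically significant laboratory values are followed (10.1). What is lost is the scheduled tests.

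**Power.** A reader might infer a material loss of power that the fix would recover. The figures do not establish one. They depend on one or two assumed subjects, on loss confined to the active arm in the two larger cases, and on rates for a superseded endpoint (at least 40% reduction at Week 16). SAP 11 says no data exist for the current one. Gastrointestinal effects are not expected at topical exposure (Protocol 3), and the earlier topical phase 2 study reported no drug-related events (Protocol 3.1). The sample size re-estimation in SAP 10 could also restore power.

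**Scoring.** Counting subjects who stop for intolerance as failures can be defended and is conservative for the active arm. SAP 5.5 adds best-case, worst-case and multiple-imputation sensitivity analyses. These help, but they do not replace observed outcomes.

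**Conclusion.** The seven-day conflict stands on the text alone. Section 8.8.8 and Sections 7.6 and 7.7 give one subject two incompatible mandatory instructions. A subject removed before Visit 6 normally becomes a non-responder on the primary and key secondary endpoints and also lacks Week 16 data.

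The diarrhea sentence is not an error. Keeping those subjects in follow-up is a cheap improvement.

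The size is unknown and may be small. Losing one or two active-arm subjects would move illustrative power from 77.7% to 73.4% or 68.6%. With equal loss in both arms the gain from keeping subjects may be nil or slightly negative. The case for the change therefore rests on consistency and complete outcome data. It should be made, and confidence in its practical importance is moderate.

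**What to change.** **Required for consistency.** In 8.8.8, change the result of the seven-day rule from removal from the study to withdrawal from treatment, for every cause, matching 7.6 and 7.7. In 7.7, delete failure to maintain the application frequency from the reasons for study discontinuation, or move it to treatment withdrawal.

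**Recommended improvement.** Replace the study-withdrawal sentence for diarrhea with: *These subjects stop study medication and should continue scheduled visits through Visit 8 per Section 7.7, unless consent is withdrawn, the investigator judges continuation not in the subject's best interest, or another section requires study withdrawal (e.g. pregnancy, unblinding).* These exceptions preserve the exits in 7.7, 9.2.7 and 8.11.2. Leave the criteria for stopping the drug unchanged.

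**Cost.** Short edits in the protocol amendment that SAP 12 already foresees, and up to five already-scheduled visits per affected subject. One further check is needed. Completing this study is an inclusion criterion for the planned 12-month open-label study (Protocol 3), so the sponsor should confirm that the open-label study separately excludes subjects who stopped the drug for diarrhea.
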